9.2. Efficacy Analysis

Efficacy analysis is **not** applicable to this study.

9.3. Pharmacokinetic Analysis

9.3.1. Analysis Populations

The PK concentration population will be defined as all subjects who received 1 dose of PF-05221304 and in whom at least 1 plasma concentration value is reported.

The PK parameter analysis population is defined as all subjects dosed who have at least 1 of the PK parameters of primary interest.

9.3.2. Derivation of Pharmacokinetic Parameters Prior to Analysis

The plasma PK parameters for PF-05221304 following single dose administration will be derived from the concentration-time profiles as detailed in Table 5. Actual PK sampling times will be used in the derivation of PK parameters. The fraction of PF-05221304 unbound in plasma (f_u) will be determined and reported for each subject by the analytical lab.

Table 5. Plasma PK Parameters

Parameter	Definition	Method of Determination
AUC_{last}	Area under the plasma concentration-time profile from time zero to the time of the last quantifiable concentration (C_{last})	Linear/Log trapezoidal method
$AUC_{last,u}$	Unbound area under the plasma concentration-time profile from time zero to the time of the last quantifiable concentration (C_{last})	$f_u * AUC_{last}$
AUC_{inf}^*	Area under the plasma concentration-time profile from time zero extrapolated to infinite time	$AUC_{last} + (C_{last}^*/k_{el})$, where C_{last}^* is the predicted plasma concentration at the last quantifiable time point estimated from the log-linear regression analysis
$AUC_{inf,u}^*$	Unbound area under the plasma concentration-time profile from time zero extrapolated to infinite time	$f_u * AUC_{inf}^*$
C_{max}	Maximum plasma concentration	Observed directly from data
$C_{max,u}$	Unbound maximum plasma concentration	$f_u * C_{max}$
T_{max}	Time for C_{max}	Observed directly from data as time of first occurrence
$t_{1/2}^*$	Terminal half-life	$\text{Log}_e(2)/k_{el}$, where k_{el} is the terminal phase rate constant calculated by a linear regression of the log-linear concentration-time curve. Only those data points judged to describe the terminal log-linear decline will be used in the regression.
CL/F^*	Apparent clearance	Dose/AUC_{inf}
CL_u/F^*	Unbound apparent clearance	$f_u * CL/F$
V_z/F^*	Apparent volume of distribution	$\text{Dose}/(AUC_{inf} * k_{el})$
$V_{z,u}/F^*$	Unbound apparent volume of distribution	$f_u * V_z/F$

*As data permits

For list of abbreviations refer to [Appendix 1](#)

090177e190d319bb\Approved\Approved On: 29-Apr-2019 07:31 (GMT)

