1.3.3. Rationale for PF-05221304 Dose Selected

A single oral dose of 25 mg will be used in this study. This dose has been selected based on prior experience in healthy subjects and also taking into account safety considerations for the subjects with varying degrees of hepatic impairment in whom an increase in plasma PF-05221304 exposure may be observed. CCI

[REDACTED]

While the proposed dose (25 mg) is half the highest dose selected for evaluation in the Phase 2a dose-ranging study (50 mg QD), repeated dosing at 25 mg QD, CCI

[REDACTED] likely to be an efficacious dose thus viewed as an appropriate for the current study.

The dose proposed in the current study (25 mg single dose) reflects adequate safety margin compared to nonclinical toxicity studies. CCI

[Redacted]

Based on a review of effect of hepatic impairment on human pharmacokinetics for compounds cleared in a similar manner to PF-05221304 CCI mild hepatic impairment generally results in less than 2-fold increases in plasma exposure. In the same group of compounds, moderate hepatic impairment results in less than 3-fold increases in plasma exposure; however, overall, very limited clinical data is available regarding the effect of severe hepatic impairment on the pharmacokinetics of CCI substrates.¹⁰ CCI

[Redacted]

CCI

[Redacted]

090177e190d319bb\Approved\Approved On: 29-Apr-2019 07:31 (GMT)

CCI [REDACTED]

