2. STUDY OBJECTIVES AND ENDPOINTS

Primary Objective:	Primary Endpoints:
To compare the pharmacokinetics of PF-05221304 (both total and unbound) following administration of a single oral dose in adult subjects with varying degrees of hepatic impairment relative to age- and body weight-matched subjects without hepatic impairment.	PF-05221304 PK parameters derived from plasma: 
 C_{max}, AUC_{inf}, f_u, $C_{max,u}$, and $AUC_{inf,u}$.
Secondary Objectives:	Secondary Endpoints:
To compare additional pharmacokinetic parameters (both total and unbound) of PF-05221304 following administration of a single oral dose in adult subjects with varying degrees of hepatic impairment relative to age- and body weight-matched subjects without hepatic impairment.	PF-05221304 PK parameters derived from plasma: 
 T_{max}, AUC_{last}, $AUC_{last,u}$, CL/F, CL_u/F, V_z/F, $V_{z,u}/F$ and $t_{1/2}$, as data permit.
To evaluate the safety and tolerability of a single oral dose of PF-05221304 when administered to adult subjects with varying degrees of hepatic impairment relative to age- and body weight-matched subjects without hepatic impairment.	Assessment of treatment-emergent adverse events, clinical laboratory tests, vital signs, and 12-lead ECGs.

090177e190d319bb\Approved\Approved On: 29-Apr-2019 07:31 (GMT)

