9. DATA ANALYSIS/STATISTICAL METHODS

Detailed methodology for summary and statistical analyses of the data collected in this study is outlined here and further detailed in a statistical analysis plan (SAP), which will be maintained by the sponsor. The SAP may modify what is outlined in the protocol where appropriate; however, any major modifications of the primary endpoint definitions or their analyses will also be reflected in a protocol amendment.

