6.3. Other Endpoints

6.3.1. PK Endpoints

Blood samples for PK analysis of PF-05221304 will be taken according to the Schedule of Activities given in the protocol.

The following PK parameters will be calculated for PF-05221304 (if possible) from the concentration-time data using standard non-compartmental methods:

Table 3. Noncompartmental PK Parameters

PK Parameter	Analysis Scale	PF-05221304	Definition
AUC_{last}	ln	A, D	Area under the plasma concentration-time profile from time zero to the time of the last quantifiable concentration (C_{last})
$AUC_{last,u}$	ln	A, D	Unbound area under the plasma concentration-time profile from time zero to the time of the last quantifiable concentration (C_{last})
AUC_{inf}^*	ln	A, D	Area under the plasma concentration-time profile from time zero extrapolated to infinite time
$AUC_{inf,u}^*$	ln	A, D	Unbound area under the plasma concentration-time profile from time zero extrapolated to infinite time
C_{max}	ln	A, D	Maximum plasma concentration
$C_{max,u}$	ln	A, D	Unbound maximum plasma concentration
T_{max}	R	D	Time for C_{max}
$t_{1/2}^*$	R	D	Terminal half-life
CL/F^*	ln	A, D	Apparent clearance
CL_u/F^*	ln	A, D	Unbound apparent clearance
V_z/F^*	ln	A, D	Apparent volume of distribution
V_{z_u}/F^*	ln	A, D	Unbound apparent volume of distribution
Fu^+	R	D	Fraction unbound

Key: A=analyzed using statistical model, D=displayed with descriptive statistics,
ln=natural-log transformed, R=raw (untransformed), *=if data permits; u=unbound fraction
+ = Reported in eNCA as protein free fraction.

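### Protocol Table 5 multiplies by fu to get CLu/F and Vz,u/F; its own AUCinf,u, CL/F and Vz/F rows imply division by fu

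*Protocol*

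**What the plan says.** Protocol 9.3.2 makes Table 5 the derivation rule: "The plasma PK parameters for PF-05221304 following single dose administration will be derived from the concentration-time profiles as detailed in Table 5". The rows that matter here are:

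- AUCinf,u = fu × AUCinf
- CL/F = Dose/AUCinf
- Vz/F = Dose/(AUCinf × kel)
- CLu/F, defined as "Unbound apparent clearance", = fu × CL/F
- Vz,u/F, defined as "Unbound apparent volume of distribution", = fu × Vz/F

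One fu per subject is reported by the analytical laboratory.

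Protocol Section 2 lists CLu/F and Vz,u/F among the endpoints of the secondary objective "To compare additional pharmacokinetic parameters (both total and unbound) of PF-05221304 following administration of a single oral dose", where the data allow. Protocol 9.3.3 and SAP 8.2 (Table 4) summarise both descriptively by cohort.

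SAP 6.3.1 says only that parameters are calculated "from the concentration-time data using standard non-compartmental methods". SAP Table 3 names and defines them without formulas. It marks both as A, D on the natural-log scale, where the key reads "A=analyzed using statistical model, D=displayed with descriptive statistics".

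**The concern.** Multiplying by fu is right for a concentration or an AUC. It is wrong for a quantity with AUC in the denominator: when AUC is scaled down by fu, clearance and volume scale up by 1/fu. The CLu/F and Vz,u/F rows appear to have carried the multiplication over from the AUC and Cmax rows.

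An analyst who follows Table 5 would report wrong values for two named secondary endpoints. The error cancels between cohorts only if fu is the same in each, and the study does not assume that: it measures fu in every subject and makes it a primary endpoint. Because the dose is fixed, the report could show AUCinf,u and CLu/F both rising in the same cohort, which cannot happen.

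**Working it through.** **Inputs.** The formulas are those of Protocol Table 5, and the dose is 25 mg (Protocol 5.5). The documents give no value of fu and no cohort ratio of fu, so those below are assumptions. For AUCinf, Protocol 1.3.3 reports, for compounds cleared in a similar way, less than 2-fold increases in mild impairment, and says that "moderate hepatic impairment results in less than 3-fold increases in plasma exposure". The range 1 to 3 is used here.

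**Per subject.** Put the table's AUCinf,u into its own definitions of clearance and volume:

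- CLu/F = Dose/AUCinf,u = Dose/(fu × AUCinf) = (CL/F)/fu
- Vz,u/F = Dose/(AUCinf,u × kel) = (Vz/F)/fu

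As written divided by correct = (fu × CL/F)/((CL/F)/fu) = fu², and the same for Vz,u/F. This is 0.25 at fu = 0.5, 0.01 at fu = 0.1 and 0.0001 at fu = 0.01. The two rules agree only at fu = 1.

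**Dose check.** Clearance times AUC should return the dose. The total rows do: CL/F × AUCinf = Dose. The unbound rows as written give CLu/F × AUCinf,u = fu² × Dose, so at fu = 0.1 they return 0.01 × 25 = 0.25 mg of the 25 mg given.

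**Between cohorts.** Let a and r be the Test/Reference ratios of geometric mean AUCinf and fu. The CLu/F ratio is r/a as written and 1/(a × r) when correct, so the error is r²: 1.56, 2.25 and 4.00 at r = 1.25, 1.5 and 2.

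CLu/F ratio, as written vs correct:

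| a | r = 1.25 | r = 1.5 | r = 2 |
|---|---|---|---|
| 1 | 1.25 vs 0.80 | 1.50 vs 0.67 | 2.00 vs 0.50 |
| 1.5 | 0.83 vs 0.53 | 1.00 vs 0.44 | 1.33 vs 0.33 |
| 2 | 0.63 vs 0.40 | 0.75 vs 0.33 | 1.00 vs 0.25 |
| 3 | 0.42 vs 0.27 | 0.50 vs 0.22 | 0.67 vs 0.17 |

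For r > 1, the direction reverses exactly when 1/r < a < r. At a = r a real fall shows as no change, and for a > r the fall is understated. At r = 1 the cohort ratio is right and only the absolute values are wrong.

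**Volume.** With k the Test/Reference ratio of kel, the Vz,u/F ratio is r/(a × k) as written and 1/(a × k × r) when correct. The error is again r², and for r > 1 reversal needs 1/r < a × k < r. With a = 2, k = 0.5 and r = 1.5 (assumed), the rule gives 1.5/1 = 1.50 instead of 1/1.5 = 0.67.

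**The case against.** The strongest reply concerns consequence. The protocol and SAP texts do not include the two parameters in the ANOVA lists, the regressions or the individual-parameter plots. There is no hypothesis test and no decision rule. AUCinf,u is derived correctly, is a primary endpoint and is modelled, and at a fixed dose it holds the same information as a correct CLu/F. Since fu, CL/F and Vz/F exist for every subject, wrong values could be recomputed later. All of this stands, and it keeps the point well below anything that threatens the primary objective.

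A second reply is that the SAP's appeal to standard methods leaves an analyst free to divide by fu. It does, but it does not say so. Table 5 is the only explicit formula in either document, and a correct result should not depend on someone quietly departing from it.

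Third, no row states that CLu/F equals Dose/AUCinf,u, so the conflict appears only once the usual meaning of unbound clearance is supplied. That is true, but the documents offer no other meaning, and the table's own label points to this one.

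Finally, the fu values and ratios are assumed, and in the table reversal occurs only where the rise in fu exceeds the rise in AUCinf; no cell at a = 2 or 3 reverses. That is correct. The factors fu² and r² are exact whatever the values turn out to be.

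**Conclusion.** The two formulas are wrong as written. The error is exactly fu² in each subject's CLu/F and Vz,u/F, and exactly r² in the Test/Reference ratio of geometric means. Whether a cohort comparison is understated, masked or reversed depends on r and a (and on k for volume), which are unknown at planning. The conclusion rests on Table 5's own definitions and on reading unbound clearance and volume as referring to unbound exposure.

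The scope is limited to two secondary endpoints that are mainly described. The primary endpoints and the sample size, which is based on AUCinf, are unaffected. It should be fixed. Whether the wrong values would also enter a model is unsettled: SAP Table 3 flags both parameters for modelling, while SAP 8.2 does not list them for the ANOVA. The same mismatch affects CL/F and Vz/F.

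**What to change.** Add to SAP Table 3:

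- CLu/F = Dose/AUCinf,u = (CL/F)/fu
- Vz,u/F = Dose/(AUCinf,u × kel) = (Vz/F)/fu

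Protocol Section 9 allows this: "The SAP may modify what is outlined in the protocol where appropriate". It calls for a protocol amendment only for major changes to the definition or analysis of the primary endpoint, and these are secondary.

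Correct the two cells of Protocol Table 5 at the next amendment. That edit needs IRB/EC approval (Protocol 12.1), so it need not trigger an amendment by itself.

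In the same SAP revision, say whether the modelling flag in SAP Table 3 is intended for CLu/F and Vz,u/F (and for CL/F and Vz/F), and make SAP 8.2 agree.

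The cost is two formulas and one clarification, with no new data and no effect on subjects.

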9.3.3. Statistical Methods

The effect of varying degrees of hepatic impairment on PK parameters will be assessed by constructing 90% confidence intervals around the estimated difference between each of the Test (impaired) cohorts and the Reference (without hepatic impairment) cohort using a one-way ANOVA model based on natural log transformed data.

One-way analysis of variance (ANOVA) will be used to compare the natural log transformed PF-05221304 AUC_{inf} , AUC_{last} and C_{max} , unbound AUC_{inf} ($AUC_{inf,u}$), unbound AUC_{last} ($AUC_{last,u}$), and unbound C_{max} ($C_{max,u}$), as data permit, for each of the hepatic impairment classification cohorts (Test) to the cohort without hepatic impairment (Reference). Estimates of the adjusted mean differences (Test-Reference) and corresponding 90% confidence intervals will be obtained from the model. The adjusted mean differences and 90% confidence intervals for the differences will be exponentiated to provide estimates of the ratio of adjusted geometric means (Test/Reference) and 90% confidence intervals for the ratios.

CCI

[figure not shown]
The PF-05221304 PK parameters C_{max} , AUC_{last} , AUC_{inf} , f_u , T_{max} , $t_{1/2}$, CL/F , V_z/F , $AUC_{inf,u}$, $AUC_{last,u}$, $C_{max,u}$, CL_u/F , and V_{zu}/F will be summarized descriptively by hepatic function cohort. Individual PF-05221304 concentrations will be listed and summarized descriptively by nominal PK sampling time and hepatic function cohort. Individual subject and summary profiles (median and means) of the concentration-time data will be plotted by treatment for both total plasma PF-05221304 and unbound PF-05221304. For summary statistics and summary plots by sampling time, the nominal PK sampling time will be used; for individual subject plots by time, the actual PK sampling time will be used. PF-05221304 AUC_{inf} , AUC_{last} , C_{max} , $AUC_{inf,u}$, $AUC_{last,u}$, and $C_{max,u}$ individual subject parameters will be plotted by hepatic function cohort.

Linear regression may be used to analyze the potential relationship between appropriate PK parameters (eg CL/F and V_z/F) and hepatic function (eg, serum albumin concentration, or prothrombin time). Estimates of the slope and intercept, together with their precision (90% confidence interval [CI]), and the coefficient of determination will be obtained from the model.

Plots of PK parameters (CL/F and V_z/F) versus hepatic function (eg, serum albumin concentration, or prothrombin time) will be constructed. A regression line and 90% confidence region for the PK parameters and hepatic function will be included.

9.4. Pharmacodynamic Analysis

Not applicable for this study.

9.6. Safety Analysis

During the study conduct, adverse events, ECGs, blood pressure, pulse rate, and safety laboratory data will be reviewed and summarized on an ongoing basis during the study to evaluate the safety of subjects. Any clinical laboratory, ECG, BP, and pulse rate abnormalities of potential clinical concern will be described. Safety data will be presented in tabular and/or graphical format and summarized descriptively, where appropriate. **In the study report**, for vital signs and ECGs, comparison will be made to the predose collections on Day 1.

Medical history and physical examination information, as applicable, collected during the course of the study will be considered source data and will not be required to be reported, unless otherwise noted.

9.6.1. Electrocardiogram Analysis

During study conduct as well as reporting of study results, baseline will be defined as 12-lead ECGs data collected on Day 1 prior to dosing of IP. Changes from baseline for the ECG parameters QT interval, heart rate, QTcF interval, PR interval and QRS interval, will be summarized by time.

The number (%) of subjects with maximum post dose QTcF values and maximum increases from baseline in the following categories will be tabulated by regimen:

	Borderline (msec)	Prolonged (msec)
Absolute Value	≥450 - <480	≥480
Absolute Change	30-<60	≥60

In addition, the number of subjects with corrected and uncorrected QT values ≥500 msec will be summarized.

090177e190d319bb\Approved\Approved On: 29-Apr-2019 07:31 (GMT)

9.7. Interim Analysis

No formal interim analysis will be conducted for this study. The sponsor may conduct reviews of the data during the course of the study for the purpose of safety assessment, facilitating PK modeling, and/or supporting clinical development.

9.8. Data Monitoring Committee

This study will not use a data monitoring committee (DMC).

10. QUALITY CONTROL AND QUALITY ASSURANCE

Pfizer or its agent will conduct periodic monitoring visits during study conduct for studies conducted at non-Pfizer investigator sites, to ensure that the protocol and Good Clinical Practices (GCPs) are being followed. The monitors may review source documents to confirm that the data recorded on CRFs are accurate. The investigator and institution will allow Pfizer monitors/auditors or its agents and appropriate regulatory authorities direct access to source documents to perform this verification. This verification may also occur after study completion.

During study conduct and/or after study completion, the investigator site may be subject to review by the IRB/EC, and/or to quality assurance audits performed by Pfizer, or companies working with or on behalf of Pfizer, and/or to inspection by appropriate regulatory authorities.

The investigator(s) will notify Pfizer or its agents immediately of any regulatory inspection notification in relation to the study. Furthermore, the investigator will cooperate with Pfizer or its agents to prepare the investigator site for the inspection and will allow Pfizer or its agent, whenever feasible, to be present during the inspection. The investigator site and investigator will promptly resolve any discrepancies that are identified between the study data and the subject's medical records. The investigator will promptly provide copies of the inspection findings to Pfizer or its agent. Before response submission to the regulatory authorities, the investigator will provide Pfizer or its agents with an opportunity to review and comment on responses to any such findings.

It is important that the investigator(s) and their relevant personnel are available during the monitoring visits and possible audits or inspections and that sufficient time is devoted to the process.

11. DATA HANDLING AND RECORD KEEPING

11.1. Case Report Forms/Electronic Data Record

As used in this protocol, the term CRF should be understood to refer to either a paper form or an electronic data record or both, depending on the data collection method used in this study.

A CRF is required and should be completed for each included subject. The completed original CRFs are the sole property of Pfizer and should not be made available in any form to third parties, except for authorized representatives of Pfizer or appropriate regulatory authorities, without written permission from Pfizer.

The investigator has ultimate responsibility for the collection and reporting of all clinical, safety, and laboratory data entered on the CRFs and any other data collection forms (source documents) and ensuring that they are accurate, authentic/original, attributable, complete, consistent, legible, timely (contemporaneous), enduring, and available when required. The CRFs must be signed by the investigator or by an authorized staff member to attest that the data contained on the CRFs are true. Any corrections to entries made in the CRFs or source documents must be dated, initialed, and explained (if necessary) and should not obscure the original entry.

In most cases the source documents are the hospital or the physician's chart. In these cases, data collected on the CRFs must match those charts.

In some cases, the CRF may also serve as the source document. In these cases, a document should be available at the investigator site and at Pfizer that clearly identifies those data that will be recorded on the CRF, and for which the CRF will stand as the source document.

11.2. Record Retention

To enable evaluations and/or inspections/audits from regulatory authorities or Pfizer, the investigator agrees to keep records, including the identity of all participating subjects (sufficient information to link records, eg, CRFs and hospital records), all original signed informed consent documents, copies of all CRFs, safety reporting forms, source documents, detailed records of treatment disposition, and adequate documentation of relevant correspondence (eg, letters, meeting minutes, and telephone call reports). The records should be retained by the investigator according to the ICH guidelines, according to local regulations, or as specified in the clinical study agreement (CSA), whichever is longer.

If the investigator becomes unable for any reason to continue to retain study records for the required period (eg, retirement, relocation), Pfizer should be prospectively notified. The study records must be transferred to a designee acceptable to Pfizer, such as another investigator, another institution, or to an independent third party arranged by Pfizer.

Investigator records must be kept for a **minimum of 15 years** after completion or discontinuation of the study or for longer if required by applicable local regulations.

The investigator must obtain Pfizer's written permission before disposing of any records, even if retention requirements have been met.

